**Table E.3: Recommended Procedures to Rule-out Contraindications for LP and Procedures to Minimize Risks\***

Recommended Procedures	Risk Factors

Rule out LP contraindication
 
 
1. Brain imaging before LP in case of:           
 
a. an intracranial lesion with mass effect
 
b. abnormal intracranial pressure
 
c. tonsillar herniation is suspected
 
d. recent seizures
 
e. impaired consciousness
 
f. papilledema
 
 
 
2. Check platelet and coagulation status (platelet > 40 X 10^9/L; INR <1.5)
 
3. Check medications before LP
 
	
Coagulopathy Uncorrected bleeding diathesis Anti-coagulant medication

Patient-related risk factors:
 
 
• Determine risk profile and inform patient before and during LP procedure
 
	

Procedures to Minimize Risk
 
 
1. 25G atraumatic needle; small needle/atraumatic needle
 
2. <4 LP attempts
 
3. Passive withdrawal
 
4. Lateral recumbent position
 
1. Collections up to 30 mL
 
	
Post-LP Headache, back pain, post-LP complaints,

## Appendix F: Assessments Associated with Rimiducid in Treatment of GVHD

Triplicate ECG: at pre-dose only.  
Taken ~5 min prior to blood draws.

ECG: Should be taken ~5 min prior to blood draws.

Rimiducid PK Sample:  
2 hr sample must be taken  $\leq$  5 min prior to end of rimiducid infusion.

Cellular Kinetics Sample.

Assessments: GVHD Treatment with rimiducid			
Time Point 	BPX-501 Cellular Kinetics (CD3+/ CD19+)	Rimiducid PK (plasma)	ECG 
Pre-Dose ( $\leq$ 4 hr)	✓	✓	✓ (triplicate)
30 minutes	✓	✓	✓
2 hr	✓ 	✓ 	✓
4 hr	✓	✓	✓
6 hr	✓	✓	✓
8 hr	✓	✓	✓
12 hr	✓	✓	✓
24 hr	✓	✓	✓
48 hr	✓	N/A	N/A
7 days	✓	N/A	N/A
14 days	✓ 	N/A	N/A
21 days	✓ 	N/A	N/A
28 days	✓ 	N/A	N/A

Rimiducid is infused over 2 hours. The reference point for all time points (0 hr) is the initiation of the rimiducid infusion.

The 2 hr PK must be collected  $\leq$  5 min prior to the end of the rimiducid infusion.

 After the last dose of rimiducid

 All ECG should be performed approximately  $\leq$  5 mins prior to any sample collection if there is a collection at the same time-point.

1. LIST OF ABBREVIATIONS

Table 1: List of Abbreviations

Abbreviation	Term
AE	Adverse Event
aGvHD	Acute Graft Versus Host Disease
Allo-HSCT	Allogeneic Hematopoietic Stem Cell Transplantation
AML	Acute Myeloid Leukemia
cGvHD	Chronic Graft Versus Host Disease
CNS	Clinical Network Services
CRF	Case Report Forms
CRO	Contract Research Organization
CSR	Clinical Study Report
DFS	Disease-Free Survival
ECG	Electrocardiography
eCRF	Electronic Case Report Form
EFS	Event-Free Survival
GCP	Good Clinical Practice
GvHD	Graft-Versus-Host Disease
Haplo-HSCT	HLA-haplo-identical Hematopoietic Stem Cell Transplantation
HIV	Human Immunodeficiency Virus
HLA	Human Leukocyte Antigen
ICF	Informed Consent Form
ICH	International Conference on Harmonization
IMP	Investigational Medicinal Product
IV	Intravenous
LFS	Leukemia-Free Survival
NCI CTCAE	National Cancer Institute Common Terminology Criteria for Adverse Events
NRM	Non-Relapse Mortality
PB-HSCT	Peripheral Blood Hematopoietic Stem Cell Transplantation
PBMC	Peripheral Blood Mononuclear Cell
PBSC	Peripheral Blood Stem Cell
RFS	Relapse-Free Survival

SAE	Serious Adverse Event
SAP	Statistical Analysis Plan
TRM	Transplant-Related Mortality
WHO	World Health Organization

2. INTRODUCTION

Over the last 4 decades, allogeneic hematopoietic stem cell transplantation (allo-HSCT) from an HLA-matched donor has been increasingly used to treat patients affected by life-threatening malignant or non-malignant disorders. In the absence of an HLA-matched donor, alternative donor/sources of hematopoietic stem cells such as HLA-haploidentical relatives are being increasingly used. While mature donor T cells present in the graft facilitate graft-vs-tumor (GvT) effects and immune cell reconstitution, in the context of increased immune genetic disparity between patient and donor, the T cells are also responsible for the occurrence of adverse T-cell mediated events such as graft-versus-host disease (GvHD), a severe, sometimes fatal, immune complication, which also impairs patient's immune reconstitution.

Haploidentical HSCT (typically derived from a parent or sibling) is an alternative donor option for pediatric AML patients; however, clinical outcomes have typically been limited due to graft failure, poor immune reconstitution, infection, and relapse with T-cell depletion approaches; or GVHD, relapse and transplant-related mortality (TRM) with unmanipulated grafts followed by post-transplant cyclophosphamide (Shaw PJ, Blood 2010; Ho VT, Blood 2001).

Treatment with the adjuvant polyclonal BPX-501 T cell product containing an inducible 'safety switch', in combination with a haploidentical HSCT, has the potential to address this high unmet medical need in children with high-risk malignancies or life-threatening non-malignant disorders that do not have a matched related or matched unrelated stem cell donor available.

The BPX-501 T cell product is intended to aid in engraftment, promote immune reconstitution, and potentially aid in graft-vs-leukemia (GVL) effect. In addition, the BPX-501 T cell product contains an inducible caspase-9 (iC9) safety switch, mediated by the infusion of the dimerizing agent rimiducid, that can be used to deplete alloreactive T-cells in the event of uncontrolled GvHD or other potential T-cell mediated adverse events that can occur with T-replete HSCT products (e.g., neurotoxicity). Rimiducid is an inert, lipid-permeable compound that rapidly induces dimerization and activation of the iC9 suicide gene via a drug-binding domain derived from human FK506-binding protein (FKBP), inducing apoptosis of the gene modified T cells.

This Statistical Analysis Plan (SAP) is based on the BP-004 study protocol and is intended to provide the statistical methods and summaries for the analysis of the data arising from the clinical trial (Protocol BP-004, Italy Version 10.0, 2 April 2018; United Kingdom Version 7.0,c 2 April 2018). Once completing the initial 180-day follow-up period, subjects enrolled into the Italian version of the BP-004 protocol were enrolled into a follow-up protocol, BP-404. Analyses presenting data beyond Day 180 in this SAP may therefore pull data from all three protocol sources (Italy and United Kingdom BP-004; Italy BP-404). The analysis approaches and methods outlined in this document, if different from the respective protocols, will supersede those specified in the protocol.

3. STUDY OBJECTIVE(S) AND ENDPOINT(S)

3.1. Study Objective(s)

Primary Objective:

- To determine whether infusion of the BPX-501 T cell product can enhance immune reconstitution in patients with malignant and non-malignant haematological disorders, with the potential for reducing the severity and duration of severe acute GvHD, thereby improving overall survival.

Secondary Objective:

- To evaluate the treatment of GvHD by infusion of the dimerizer drug (AP1903/rimiducid), activating the suicide gene iC9, in those subjects who present with GvHD who progress on, or do not respond to, standard of care treatment.

3.2. Study Endpoint(s)

Endpoints will be further defined in subsequent sections. Unless otherwise specified, time-to-event endpoints will be calculated from the date of HSC infusion. If a patient received more than one HSCT, the time of the last HSC infusion immediately preceding infusion with BPX-501 will be the transplant date.

Primary Endpoint:

Event-Free Survival (EFS) at 180 days. Events are defined as the first occurrence of either transplant-related mortality (TRM) for non-malignant patients or non-relapse mortality (NRM) for malignant patients, severe GvHD (Grade 2-4 acute organ GvHD or extensive/moderate-severe chronic GVHD), and life-threatening infections (Grade 4).

NB: In the BPX-501 protocols, the terminology 'extensive' chronic GvHD was used. For the purposes of the primary analysis and for the rest of this SAP, extensive chronic GvHD will be defined as moderate or severe chronic GvHD. 'Overall' chronic GvHD or chronic GvHD without a qualifier will be interpreted as mild, moderate or severe chronic GvHD.

The following secondary endpoints are in the BP-004 protocols, although additional endpoints and analyses are described below in subsequent sections of this document.

Secondary Endpoints:

- (i) Transplant-Related Mortality (TRM) in patients with non-malignant diagnoses or Non-Relapse Mortality (NRM) in patients with malignant diagnoses at 100 and 180 days
- (ii) Cumulative incidence and severity of acute GvHD (any Grade 2-4 or Grade 3-4) as well as overall and moderate-severe chronic GvHD at 180 days.
- (iii) Time to resolution of acute GvHD after administration of rimiducid
- (iv) Immune reconstitution as determined by T cell subsets up through 180 days
 - a. Absolute CD3 count
 - b. Absolute CD4 count

- c. Absolute CD8 count
- (v) Time-to-immune reconstitution defined by CD3 count > 500 cells/uL; CD4 count > 200 cells/uL; CD8 count of 200 cells/uL
- (vi) Disease-Free/chronic GvHD Survival (DFGS) defined as the first of either disease recurrence, death from any cause, or chronic GVHD
- (vii) Disease status within the following disease indications at 180 days:
 - a. Primary immune disorders as determined by CD3 T cell count ≥ 500 cells/uL and normal levels of IgA and IgM
 - b. Haemoglobinopathies as determined by incidence of RBC transfusion independence for 8 consecutive weeks and untransfused haemoglobin of ≥ 8.5 g/dL
 - c. Fanconi Anemia as determined by RBC $\geq 3,000,000$ cells/uL, neutrophil count ≥ 1500 cells/uL and platelet count $\geq 150,000$
 - d. Relapse Free Survival (RFS) in subjects with leukemia

Safety Endpoints:

Safety assessments and summaries will include reported AEs and SAEs; protocol-specified hematology; and clinical chemistry.

4. STUDY DESIGN

This phase II study is a multi-center single-arm extension study following completion of a phase I dose escalation study, where subjects were treated in a 3+3 dose escalation design.

As stated in the protocol, this study enrolled any infant (1 month-24 months), child (2-11 years) or teenager (12-18 years) with malignant hematological disorders in complete morphological remission or non-malignant hematological disorders eligible for an allogeneic transplantation and lacking either a related or unrelated HLA-matched donor or whose disease status does not allow the extensive wait for an unrelated donor. Patients will have access to a partially matched family donor who will provide PBMCs for creating the BPX-501 modified T cells as well as the HSCT.

Up to 175 pediatric patients were to be enrolled in this phase II extension trial at the dose of 1×10^6 cells/kg regardless of disease classification (malignant or non-malignant). The study follow-up for each patient will be at least 180 days.

After completing the study, eligible subjects will be enrolled in a gene therapy follow-up study for a total of 15 years. Given the various protocols referenced in this document, additional follow-up beyond 180 days is within scope of this SAP and longer-term results may be presented for supportive purposes.

4.1. Definition of Study Drugs

The study drugs are:

- BPX-501: *Donor T cells genetically modified with BPZ-1001 retroviral vector containing the iC9 suicide gene, and*
- Rimiducid (AP1903): *Dimerizer drug used in case of a patient developing GvHD*

The BPX-501 T cell infusion is administered 14 days (+/-4 days) after completion of the stem cell allograft infusion. Under certain protocol versions, subjects may have been administered BPX-501 within 21 days (+/- 14 days) after completion of the stem cell allograft infusion. Subjects with uncontrolled Grade I or II skin-only, Grade II (non-skin), III, or IV acute GvHD were eligible to receive up to three doses of rimiducid at 0.4 mg/kg as a 2-hour intravenous (I.V.) infusion. Chronic GvHD, under conditions specified by protocol, will be treated with an infusion of rimiducid in individuals who have not previously received an infusion of rimiducid.

4.2. Sample Size Considerations

This study was originally designed as a 3+3 Phase 1 dose escalation study of BPX-501, with sample size considerations based on estimating a maximum tolerated dose (MTD) and assessing preliminary safety. The study was later expanded to enroll up to 175 subjects having various diseases considered amenable to treatment with BPX-501. Power considerations were later based on the use of a non-inferiority analysis comparing patients treated with BPX-501 in the BP-004 study to the cohort of subjects enrolled at largely overlapping study centers in the C-004 and CP-004 studies who received a matched unrelated donor (MUD) transplant (with two additional sites Italian brought on under C-004). A non-inferiority margin of 10% was pre-specified.

Sample size considerations were updated pending reporting of interim results (Algeri et al, ASH 2018). Assuming a sample size of 100 efficacy-evaluable subjects and a baseline EFS rate at day

180 of 88% in subjects receiving a MUD transplant, and assuming a sample size of 160 efficacy-evaluable subjects and an EFS rate at day 180 of 91% in subjects receiving BPX-501, this study has approximately 91% power to claim non-inferiority of BPX-501 relative to a MUD transplant based on a test of difference of proportions. Assuming a sample size of 70 efficacy-evaluable subjects receiving a MUD transplant, and assuming a sample size of 140 efficacy-evaluable subjects receiving BPX-501, this study has approximately 84% power to claim non-inferiority of BPX-501 relative to a MUD transplant based on a test of difference of proportions. Power calculations were performed using PASS software and checked using the gsDesign package in R.

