6. STATISTICAL METHODS AND DATA HANDLING

6.1. Analysis Populations

The following analysis populations are defined for the study:

(i) *Enrolled Population (EP)* – Defined as all patients who signed informed consent, were assessed for inclusion/exclusion criteria during the screening period, and who were considered eligible for enrollment and post-enrollment follow-up. This population will be used to present overall study disposition data and for summarizing the total number of patients screened and considered eligible for the study.

(ii) *HSCT Safety Population (HSP)* – Defined as all patients in the enrolled population (EP) who received Hematopoietic Stem Cell Transplantation (HSCT). Only SAEs were reported in subjects prior to receiving BPX-501. The HSP therefore represents the analysis population for certain analyses of SAEs as well as disposition and outcomes in subjects who did not go on to receive BPX-501 for any reason.

(iii) *BPX-501 Safety Population (BSP)* – Defined as all patients who received HSCT and went on to receive any dose of BPX-501. Unless otherwise specified, this will be the default primary safety analysis population.

(iv) *Intent-to-treat Population (ITT)* – Given that this is a single-arm study, a “Full Analysis Set” (FAS) population is proposed to serve as the ITT population from which to provide estimates of treatment effects in subjects receiving BPX-501. The FAS/ITT population includes all patients treated with HSCT who received BPX-501 at the dose of 1×10^6 cells/kg.

(v) *Per Protocol Populations (PP)* – Defined as all patients in the ITT/FAS analysis population who were infused with BPX-501 at the dose of at least 1×10^6 cells/kg within a dosing around Day 14 (+/- 4 days) or Day 21 (+/- 14 days) after HSCT. The primary and key secondary efficacy analyses may be repeated on the PP populations as a means of characterizing the robustness of any outcome results.

(vi) *Rimiducid Population (RP)* – Defined as all patients who received at least one dose of rimiducid for the treatment of acute or chronic GvHD.

(vii) *Rimiducid Pharmacokinetics Population (RPK)* – Defined as all patients who received at least one dose of rimiducid for the treatment of acute or chronic GvHD and have a plasma sample to measure rimiducid concentrations over time.

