6.2. Statistical and Analytical Methods

6.2.1. General Statistical Approach Summaries

Data will be summarized with respect to each of the performance outcomes assessed, pooled across all the investigative sites and, in many cases, stratified by type of disorder (malignant or non-malignant). Continuous endpoints will be summarized using the number of observations, mean, median, standard deviation or interquartile range, and minimum and maximum values. Categorical endpoints will be summarized using the number of observations and percentages. Time-to-event assessments will be summarized using either Kaplan-Meier or Nelson-Aalen statistical techniques, as appropriate, with display of parameter estimates at pre-defined timepoints along with the number of censored observations. Unless otherwise stated, confidence intervals will be constructed at the 95% confidence level. Any potential statistical tests will be two-sided, with type 1 error rate of 5%. *P*-values will be rounded to three decimal places, with *p*-values less than 0.001 will be reported as <0.001, and *p*-values greater than 0.999 will be reported as >0.999.

Data listings will be sorted by treatment, dose, site identification number, subject identification number and visit.

The primary analysis is planned to be conducted after the last patient enrolled has either completed 180 days of follow-up on study or withdraws from the study prior to 180 days. Unless otherwise stated, statistical analysis will be performed using SAS statistical software (Version 9.4, unless otherwise noted). Adverse events were coded using MedDRA version 18.0. Concomitant medications were coded using World Health Organization (WHO) coding standards and the WHO 2015 drug dictionary. For key adverse events and concomitant medications, any coding changes between the versions used for analyses and more recent versions will be highlighted.

For rimiducid plasma concentration data, summary statistics will include the arithmetic mean, arithmetic standard deviation, median, minimum, maximum, and number of observations. Data listings will be provided for all subjects up to the point last evaluable sample collection. Any subjects excluded from the relevant population will be highlighted. For the calculation of summary statistics and statistical analysis, unrounded data will be used.

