6.4. Efficacy Analysis

The analysis of primary and secondary endpoints will be based on the ITT (FAS) population as the primary analysis population. Any supportive sensitivity analyses may be assessed on the PP population or other subgroup defined below. Final decisions on different exploratory subgroups will be determined prior to the time of primary analysis.

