6.4.1. Primary Efficacy Analysis

The primary efficacy endpoint is Event-Free Survival (EFS) up to 180 days using the ITT (FAS) population. Events corresponding to EFS outcome include

- Transplant-Related Mortality (TRM) for non-malignant patients or Non-Relapse Mortality (NRM) for malignant patients, defined as the time from transplant until death without evidence of recurrence or relapse,
- Severe GvHD, defined as any case of grade 3-4 acute GvHD regardless of organ involvement, any case of grade 2 acute GvHD with visceral (non-skin-only) organ involvement, or any case of moderate-severe chronic GvHD, and
- Life-threatening infections (Grade 4).

For patients with multiple events, the event that occurs first and the corresponding time will be used for the EFS. Subsequent EFS-qualifying events will be provided in a listing in order to describe longer-term outcomes observed in patients with a primary EFS event. Patients who do not experience an EFS-qualifying event will be censored on the last day of observation. EFS will be calculated from the date of HSCT transplant defined above.

Kaplan-Meier techniques will be used to estimate EFS at day 180. When estimable, additional summary statistics will include the median, minimum, maximum, the 25th and 75th percentiles of EFS along with the number of events and censored observations. Kaplan-Meier plots with descriptive summary statistics will be presented along with the number of patients at risk at various time points.

An additional sensitivity analysis of EFS may be performed using an expanded definition of EFS-qualifying events to include patients with skin-only grade 2 acute GvHD.

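### SAP 4.2 states about 91% and 84% power for a non-inferiority claim against a matched-unrelated-donor cohort, but no analysis in this SAP makes that comparison or refers to one

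*SAP*

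**What the plan says.** SAP 4.2 bases its power on comparing BPX-501 patients in BP-004 with MUD recipients enrolled in C-004 and CP-004. It states: "A non-inferiority margin of 10% was pre-specified". The Day-180 EFS rates assumed are 88% (MUD) and 91% (BPX-501), the method is a test of difference of proportions, and the conclusion for 100 MUD and 160 BPX-501 patients is that "this study has approximately 91% power to claim non-inferiority of BPX-501 relative to a MUD transplant". For 70 and 140 patients the figure is about 84%. The counts are of patients described as evaluable for efficacy: "assuming a sample size of 160 efficacy-evaluable subjects".

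The analysis sections read differently:

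- Section 6.1 defines seven populations, all within BP-004. The primary one is limited to BPX-501 recipients: "The FAS/ITT population includes all patients treated with HSCT who received BPX-501" at the stated dose.
- Section 6.4 says: "The analysis of primary and secondary endpoints will be based on the ITT (FAS) population as the primary analysis population".
- Section 6.4.1 says: "Kaplan-Meier techniques will be used to estimate EFS at day 180".
- Section 6.2.1 has only a general rule on error rate: "Any potential statistical tests will be two-sided, with type 1 error rate of 5" percent. Section 4.2 gives no alpha.
- Section 6.6 reports no major change from the protocol and does not mention the MUD comparison.

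**The concern.** A power statement should describe the operating characteristics of a planned analysis. Here it describes a two-cohort test, while the plan describes a one-cohort estimate. A statistician who follows this SAP exactly produces an EFS curve for BPX-501 patients and nothing that can be set against a 10-point margin.

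Two of the SAP's own rules make this more than a missing detail. Section 2 says that the SAP's methods prevail over the protocols where they differ. If the BP-004 protocol does plan the comparison, a reader cannot tell whether the single-arm plan replaces it. Section 7.1 requires additional unplanned analyses to be documented and justified in the study report. On the face of this SAP, a later MUD comparison would fall under that rule, which would weaken its standing as pre-specified.

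**Working it through.** **Inputs.** From SAP 4.2: MUD rate 0.88, BPX-501 rate 0.91, margin 0.10, sizes (MUD/BPX-501) 100/160 and 70/140. The rates are not restated for 70/140, so I assume that they carry over. I take alpha as one-sided 0.025, from the general two-sided 5% rule in 6.2.1. This too is an assumption, because 4.2 gives no alpha.

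**Reproducing the stated power.** Power = Φ[(0.91 − 0.88 + 0.10 − 1.96·SE0)/SE1].

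- SE1 = √(0.88·0.12/nM + 0.91·0.09/nB). For 100/160 this is √(0.001056 + 0.000512) = 0.0396. For 70/140 it is √(0.001509 + 0.000585) = 0.0458.
- SE0 is the standard error used in the test. Unpooled, it equals SE1. Pooled, it is √[p̄(1 − p̄)(1/nM + 1/nB)], with p̄ = 0.8985 and 0.9000, which gives 0.0385 and 0.0439. With restricted maximum likelihood under a true difference of −0.10, it is 0.0385 and 0.0421.

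| Test statistic | 100/160 (stated 91%) | 70/140 (stated 84%) |
|---|---|---|
| Unpooled | 90.7% | 81.1% |
| Pooled | 91.6% | 83.1% |
| Restricted MLE | 91.6% | 85.0% |

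Pooled and restricted-MLE tests come close to both stated figures; unpooled falls 2.9 points short at 70/140. One-sided 0.05 with a continuity correction c = 0.5(1/nM + 1/nB) also comes close. Φ[(0.13 − 0.0081)/0.0396 − 1.645] = 92.4% and Φ[(0.13 − 0.0107)/0.0458 − 1.645] = 83.2%. The figures are sound for a two-group test, but they do not identify which alpha and statistic were used.

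**Looking for the analysis.**

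| Element needed | Where it would be | What is there |
|---|---|---|
| MUD population | 6.1 | None |
| Definition of efficacy-evaluable | 6.1 | None of the seven populations has this name |
| EFS difference and decision rule | 6.4.1 to 6.4.3, 6.7 | None; single-arm estimates only |
| Handling of non-randomised differences | 6.4 to 6.7 | None |
| Output | 7.1.1 | No MUD table, figure or listing |
| Reference to another document | 6.7 | Only for population PK and further exploratory laboratory work |

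**What separates the two analyses.** At the planning rates and without censoring:

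- The single-arm half-width is 1.96·√(0.91·0.09/n), which is 4.4 points at n = 160 and 4.7 at n = 140.
- The half-width of the difference is 1.96·SE1 (unpooled), which is 7.8 points (100/160) and 9.0 points (70/140).

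**What the non-inferiority rule would demand.** Suppose that MUD EFS is observed at 88%. The smallest BPX-501 EFS p that meets the margin solves (p − 0.88) + 0.10 = 1.96·SE0(p).

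| Test statistic | 100/160 | 70/140 |
|---|---|---|
| Restricted MLE | 86.09% | 86.86% |
| Unpooled | 86.30% | 87.39% |
| Pooled | 86.40% | 87.45% |

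The threshold is thus about 86.1% to 86.4%, or 86.9% to 87.5%, depending on the statistic. These are benchmarks only: 88% of 70 is 61.6 patients, which cannot be observed as a simple proportion.

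**The case against.** The strongest reply is that this is the SAP for BP-004, and that the MUD patients belong to other studies. One would not normally expect 6.1 to define another study's population. Section 4.4 leaves the full design description to the BP-004 protocol, and 6.6 reports no major departure from it. The comparison may be fully specified in BP-004, C-004 or CP-004 documents, none of which was supplied. This stands, and it limits the point to what this SAP contains. It does not remove the point: 4.2 attributes the power to this study, and nothing directs the reader elsewhere.

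A second reply is that much is already fixed. The comparator studies, endpoint, margin and type of test are in 4.2, and the primary population is in 6.4. That is fair. Alpha does not belong on the list, because 6.2.1 speaks only of potential tests and more than one alpha fits the stated figures.

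A third reply is that the supplied protocol is BP-404. It enrols patients beyond Day 180, and its primary endpoints are overall, disease-free and relapse-free survival at 1 and 2 years, summarised descriptively. That is correct. The MUD comparison has no bearing on those endpoints.

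**Conclusion.** The point holds for this SAP. The stated power of about 91% and 84% is attached to no analysis that the SAP plans; followed as written, it yields a single-arm Kaplan-Meier estimate. It should be fixed, and it may amount to no more than a missing cross-reference.

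A reader might go further in three ways that the documents do not support:

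- That the power is miscalculated. It reproduces under the planning rates with a pooled or restricted-MLE test at one-sided 0.025.
- That the sponsor has no plan for the comparison. The documents that might hold one were not available.
- That adjustment for non-randomised cohorts would cost a particular amount of power. The documents give no basis for an effective sample size.

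The primary population is conditional on receiving BPX-501 while EFS is counted from transplant. That is a separate matter, which arises with or without a MUD cohort, and it is not part of this conclusion.

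The half-widths and thresholds assume the planning rates, no censoring and one-sided 0.025. The thresholds also assume that MUD EFS is observed at 88%.

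**What to change.** Choose one of two routes.

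(a) If the comparison is intended, cite in 4.2 and 6.4.1 the document that specifies it. If there is none, complete it here:

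- define the MUD population and the efficacy-evaluable set;
- state the alpha and the test statistic behind 4.2;
- estimate the Day-180 EFS difference (BPX-501 minus MUD), counted from transplant in both cohorts, using the malignant and non-malignant strata;
- declare non-inferiority if the lower confidence limit exceeds −10 points;
- say how differences between the non-randomised cohorts are handled;
- add the output table to 7.1.1.

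(b) If no comparison is planned, remove the power claim. State instead the precision of the planned estimate: about ±4.4 points at n = 160 and ±4.7 at n = 140, at 91% EFS without censoring.

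Neither route needs new patients. A cross-reference is one sentence. Completing the comparison adds some analysis work and needs C-004 and CP-004 data on the same EFS components. Route (b) gives up the non-inferiority claim, so it should be used only once it is confirmed that no other document plans it.
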